The Executive Committee will be the major decision-making body with primary responsibility for study management. The committee will direct operational aspects of the study, decide on all proposed changes in the protocol, and decide on all uses of study data. In the latter role, the committee will make all decisions regarding publication policies and will review all manuscripts and abstracts from the study and approve these for submission. Initially, the Executive Committee will have monthly conference calls, with the frequency of ongoing conference calls to be decided by the Executive Committee members.

Data Monitoring Committee:

Since the VADT-FS is an observational study and includes no research related clinical interventions, the main task of the Data Monitoring Committee will be to assure data quality, ongoing blinding of the study results, adherence to the pre-specified analysis plan, overall study progress and whether assumptions regarding statistical power are met. In addition to overseeing the integrity of scientific quality of data, this committee will examine unblinded analyses of primary and secondary endpoints every year. Since the intervention will no longer be in effect there will be no interim monitoring rule. The study biostatistician will present the Committee with interim reports and unblinded outcome data annually. The study Chairs and other Executive Committee members will not be privy to these interim reports. The previous CSP #465 Data Monitoring Committee was asked to participate and continues to serve as the DMC for the follow-up study.

Endpoint Evaluation Committee

The composition and procedures of this Committee were outlined above under *Measuring Endpoints*.

Analysis Plan.

Statistical power

We considered a 20% reduction in primary events to be a reasonable goal of intensive glycemic control over the anticipated 15-year study time period. This effect size was chosen by taking into consideration both the probability of observing an effect of that size given the level of achieved A1c separation, and the perceived value to the patient of this level of benefit relative to the risk and burden of intensive glycemic control. In addition, a 20% reduction is consistent with the lower limits of the 95% confidence intervals of the level of association between A1c and cardiovascular events reported in observational analyses (Nathan, 2005; Selvin, 2004).

Given the current rate of overall events observed in the VADT, Table 2. below shows the expected statistical power that the VADT-FS will have for its primary and secondary outcome measures. As a continuous measure, statistical power for health related quality of life will be even better.

Table 2. Power Calculations for VADT-FS*

	Overall Study Event Rate	At 6 year Follow-up (end of VADT)	At 10 year Follow-up†	At 15 year Follow-up†
	(events per 1000 person-years)	Statistical Power to detect a Hazards Ratio of 0.8*		
CV events (Primary Outcome)‡	51.9	0.93	0.98	0.99
CV Mortality	5.5	0.00	0.08	0.31
Micro-vascular events§	31.4	0.00	0.35	0.71
Total Mortality	13.7	0.00	0.14	0.43

* All power calculations are for 2-tailed testing and assume $\alpha=0.05$.

† Estimates assume 85% retention of study subjects from the VADT and attrition due to mortality.

‡ Major CV events include: non-fatal heart attack, non-fatal stroke, new CHF, amputation for ischemic diabetic gangrene, or CV death).

§ Microvascular events include: end-stage renal disease, irreversible severe visual impairment [i.e., excludes visual acuity problems correctable by cataract surgery], or amputation for ischemic diabetic gangrene).

Update

Given the achieved sample size of the VADT-FS Main Cohort (N= 1031 as of July 31, 2011), the updated power at 15-year follow-up is now 86.3%, which is still excellent. Based on additional information, the power for detecting effects for CV and total mortality are better than what we previously thought but are still under 30%. Although power for mortality is still poor, these results will be useful for inclusion in future meta-analyses.

Objective #1: To determine the long term effects of intensive glycemic control in type 2 diabetes on major cardiovascular complications (primary outcome).

The primary outcome measure is the time to the first of any of the following events: nonfatal heart attack, nonfatal stroke, new congestive heart failure, amputation for ischemic gangrene, or cardiovascular death. The assessment of endpoints comparing the

original study glycemic treatment arms will be analyzed as per original intent-to treat using methods identical to the current VADT study. Life table methods and the log-rank test will be used to compare complication-free survival between the two treatment groups. (Halpern, 1987) Preliminary analyses suggest that the treatment groups were quite similar on important factors at baseline, so we do not anticipate needing to use Cox proportional hazards regression to control for baseline confounding. (Halpern, 1987) However, Cox proportional hazards regression methods will be used to perform a time-dependent covariate survival analysis of the primary outcome. This analysis will adjust for risk factors post intervention such as A1 c, weight, BMI, SPB, DBP, cholesterol, HDL, LDL, use as time dependent covariates. The progress report will include these post-intervention risk factors summarized over time as available through database search.

Objective #2. To determine the long term effects of intensive glycemic control in type 2 diabetes on four secondary outcomes: a) cardiovascular mortality, b) major microvascular complications, c) health-related quality of life, d) total mortality, and e) major microvascular or macrovascular (end-stage renal disease, amputation for either ischemic or non-ischemic gangrene, CV-related death, or nonfatal MI, stroke, or new CHF). Statistical analyses for secondary outcomes will be identical to those used for the primary outcome, with the exception of microvascular complications and health related quality of life. Since one of the microvascular complications, severe visual impairment, is from the annual survey, survival analysis is not appropriate for the inaccuracy of the time of the record but logistic regression analysis. Since health related quality of life is a continuous measure, survival analysis will not be appropriate for this secondary outcome. The Student t-test will be used to evaluate for differences in mean quality-of-life scores in the two treatment arms, with use of robust methods if there is evidence that variance estimates vary between the two groups. It is well known that if there is a substantial difference in survival between intervention groups, health related quality of life results can be misleading unless the survival differences are accounted for. Therefore, if there are substantial differences in survival between treatment groups, an alternative analysis accounting for missing data due to mortality is a Bayesian imputation approach. (Revicki, 2001) Again, since substantive differences in baseline attributes did not occur, we do not feel that controlling for potential confounders using ordinary least squares regression is necessary.

Update

We have added a composite measure “Major Microvascular & Macrovascular Events, which is simply an aggregate of the primary outcome with the secondary outcome for microvascular outcomes. Statistical analyses for secondary outcomes will be identical to those used for the primary outcome, with the exception of health related quality of life. Since health related quality of life is a continuous measure, survival analysis will not be appropriate for this secondary outcome. The Student t-test will be used to evaluate for differences in mean quality-of-life scores in the two treatment arms, with use of robust methods if there is evidence that variance estimates vary between the two groups. It is well known that if there is a substantial difference in survival between intervention groups, health related

quality of life results can be misleading unless the survival differences are accounted for. Therefore, if there are substantial differences in survival between treatment groups, an alternative analysis accounting for missing data due to mortality using a Bayesian imputation approach (Revicki, 2001), which will be done by Ann Arbor according to their IRB permission on mortality data collection on all VADT population except the terminated. Again, since substantive differences in baseline attributes did not occur, we do not feel that controlling for potential confounders using ordinary least squares regression is necessary. For the quality of measure, we will deal with confounding due to systematic mortality differentials between treatment arms by using selection models, as recommended in *Assessing Quality of Life in Clinical Trials: Methods and Practice* (eds. Fayer P, Hays R, April 2005.)

Update: (Early Analysis)

The major protocol amendment for the VADT-F was that a mid-point analysis would be conducted and reported, which was made and published as planned. We now plan for an early analysis to take place shortly before data is fully completed with adjudicated outcomes and locked. There is to prepare to submit an important presentation in time to take place at the American Diabetes Association (ADA) 2018 which is planned to be made in conjunction with publication of the corresponding manuscript. Below we provide the full justification for this analysis.

A major concern about an early analysis of clinical trials is that it can potentially bias investigators involved in the study protocol and thus integrity of reported data. However, this concern does not apply to this proposed early VADT-F analysis. As active intervention ceased 10 years ago at the conclusion of the VADT, and there are no longer research personnel that have clinical contact with the study subjects, there is no way for investigators to influence patient care or outcomes. The outcomes are being collected through database search and surveys. In addition, the investigators will be still blinded to the individual treatment level data, which will become available for analyses before the final presentation. Thus, the potential for bias is not a threat to the VADT-F.

On the other hand, there will be substantial benefit to the diabetes community as we present in a timely manner this important study about whether or not there is a delayed effect of the intensive treatment, and all presentations and papers will use fully completed and locked data.

We therefore believe that the benefits of an early analysis provide substantial benefit to the diabetes community and do so at essentially no risk to the integrity of the VADT-F.

Other Analysis Considerations *Interaction (Subgroup) Effects*

The improved statistical power of the VADT-FS allows us more freedom to examine interaction effects (subject baseline attributes that modify the treatment effect) than is possible in the VADT. However, our only *a priori* hypotheses regarding biological factors that may modify the treatment effect relate to patient attributes that affect the likelihood of the outcomes. As has been recently reported, in such instances it is preferable to combine risk factors into a risk score whenever feasible (which will generally dramatically improve statistical power as well as diminish problems inherent in multiple comparisons)(Brookes, 2004; Hayward, 2005). Therefore, rather than look at cardiovascular risk factors in isolation, we will combine these risk factors into the Framingham risk score (Hayward, 2006). As reported by Brookes et al, statistical power for such interaction effects is further improved if these interaction effects are examined as continuous variables using Cox proportional hazard modeling, rather than subdividing the risk score into categories.(Brookes, 2001) Consequently, we will examine whether the treatment effect is modified by a subject's 10-year risk of CV events (as predicted by a subject's baseline Framingham score), which will test whether the hazard ratio varies conditional on baseline overall CV risk.(Wilson, 1998) Similarly, we will conduct regression analyses examining for interaction effects between treatment arm and a study subject's risk of major microvascular complications, using the prediction model discussed above (Vijan, 1997).

Evaluation of Mechanisms of Action

In addition to examining interaction effects (factors that modify the intervention's effect), we will examine factors that are hypothesized to mediate the interaction effect. Whereas interaction effects are part of the experimental analysis (examining baseline [pre-randomization] subject attributes that identify individuals or groups who will benefit more or less than average), examination of potential mediating factors are observational analyses (examining factors post-treatment but prior to the occurrence of an outcome trying to better understand the treatment's mechanism(s) of action).(Hayward, 2006) There are two principle hypothesized mechanisms of action for why improved metabolic control may reduce CV events: 1) direct effects of hyper-glycemia on blood vessels and atherosclerotic disease, and 2) decreasing the prevalence of diabetic nephropathy and proteinuria (microvascular complications known to increase with hyperglycemia), which in turn reduces risk of CV events. We will examine these two factors following the methods used in the DCCT/EDIC.(Nathan, 2005) The variable examining direct hyperglycemic effects will be based upon the log of cumulative average A1c (previous observational analyses have consistently reported a log-linear association between A1c and adverse outcomes), which will be updated annually for all subjects who have not yet reached the endpoint. Markers for diabetic nephropathy previously reported to be associated with CV risk, include presence of proteinuria and estimated GFR. In addition to the log of cumulative average A1c, proteinuria and GFR, this analysis will control for a subject's other CV risk factors. (Fleiss, 1986) Cox proportional hazards regression will be used for these analyses, except for the visual impairment outcome which was not collected during the original VADT. Since time of the event is not available, logistic regression will be used for this outcome.

Missing Data

In longitudinal studies relying on survey or tests ordered in routine clinical practice, problems of missing data will almost always increase. Fortunately, our primary outcome and three of our four secondary outcomes do not rely on these data sources. However, our

analysis of health related quality of life will be limited to those subjects who have answered the survey. For those analyses of interaction effects and potential mechanisms of action, outlined above, standard multiple imputation techniques will be utilized so as to prevent diminished sample size and potential response bias due to dropping subjects with missing data on covariates. (King, 2001; Revicki, 2001; Carroll, 1995) Imputed values for a given covariate will be informed by an individual's values for all other observed covariates to be used in the regression model, as well as temporal trends in the study population and previous values for that covariate in the individual. Multiple imputation is preferable in such instances, since it accounts for the degree of precision in imputed values and therefore provides better variance estimates for all regression coefficients. (King, 2001; Clayton, 1991; Carroll, 1995; Gatsonis, 1995; Oppenheimer, 1999)

Updates

There are no anticipated changes in the planned analyses, other than the addition of the new composite secondary endpoint, "Major Microvascular & Macrovascular Events" (see Endpoints Section) except severe visual impairment, which will be analyzed independently from other outcomes using only data collected through self-administered survey questionnaire during this follow-up period since 2009.

Study Significance.

The proposed extension of the VADT Follow-up Study (VADT-FS) would capitalize on a unique opportunity to examine factors that are associated with long-term complications and mortality for people with one of the most important conditions in modern medicine, a disease that will continue to grow dramatically if current epidemiological trends continue. Given the results of the UKPDS Follow-up Study and the DCCT-EDIC study, the objectives of the VADT-FS are important to answer in order to better assess possible multiplicative temporal effects and to obtain adequate statistical power to assess mortality benefits directly. It will also provide an opportunity to assess the long-term impact of tight glycemic control on vision and renal insufficiency when tight blood pressure control is achieved, a question unanswered by previous studies.

References:

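### Table 2's primary power of 0.93, 0.98 and 0.99 does not follow from its own rate, hazard ratio and footnotes, and three unlabelled 6-year cells of 0.00 are impossible as two-sided power

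*Combined protocol and SAP*

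**What the plan says.** Under Analysis Plan, Statistical power, the plan states that "Table 2. below shows the expected statistical power that the VADT-FS will have for its primary and secondary outcome measures". The table gives one event rate per outcome (per 1000 person-years) and the power to detect a hazard ratio of 0.8:

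| Outcome | Rate | 6 years (end of VADT) | 10 years | 15 years |
|---|---|---|---|---|
| CV events (primary) | 51.9 | 0.93 | 0.98 | 0.99 |
| CV mortality | 5.5 | 0.00 | 0.08 | 0.31 |
| Microvascular | 31.4 | 0.00 | 0.35 | 0.71 |
| Total mortality | 13.7 | 0.00 | 0.14 | 0.43 |

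The footnotes add: "All power calculations are for 2-tailed testing and assume" alpha = 0.05; and, for the 10- and 15-year columns only, "Estimates assume 85% retention of study subjects from the VADT and attrition due to mortality". No sample size, allocation ratio or formula is given.

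Objective #1 fixes the type of analysis: "The primary outcome measure is the time to the first of any of the following events", compared by log-rank test, with the statement that the "original study glycemic treatment arms will be analyzed as per original intent-to treat".

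The Update under the table says that, with a Main Cohort of 1,031, "the updated power at 15-year follow-up is now 86.3" per cent. On mortality it says "the power for detecting effects for CV and total mortality are better than what we previously thought but are still under 30" per cent, and then: "Although power for mortality is still poor".

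**The concern.** The primary row looks too high for its rate. Log-rank power depends on the number of events, and 51.9 per 1000 person-years in a cohort of this size does not seem to supply enough by year 6. The three cells of 0.00 share a column with 0.93, so they cannot simply mean that follow-up has not yet begun.

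Other parts of the protocol lean on these figures. The Primary study end-point section justifies the narrower endpoint by the increased power of the follow-up study, and the Interaction (Subgroup) Effects section argues the same way. As printed, though, primary power falls from 0.93 at the end of VADT to 86.3% at 15 years. The Data Monitoring Committee is asked to check whether the power assumptions are met, and it cannot do so from a table that cannot be rebuilt. The printed figures also exaggerate what the smaller cohort costs: about 13 points (0.99 to 0.863), against about 5 (0.916 to 0.868) on one method.

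**Working it through.** **Inputs.** Rates, hazard ratio, alpha and the 85% retention are from Table 2 and its footnotes. N = 1,791 is VADT enrolment (Study Subjects). My assumptions are 1:1 allocation, a constant pooled rate, and everyone followed to year 6.

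**Formula.** For D events, power = Φ(|ln 0.8|·√D/2 − 1.96) + Φ(−|ln 0.8|·√D/2 − 1.96), with |ln 0.8| = 0.2231. Inverting it, 0.93 needs about 948 events, 0.98 about 1,294 and 0.99 about 1,476.

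**Step 1: the most events the primary rate can give** (no loss, nobody removed after an event).
- 6 years: 1791 × 6 × 0.0519 = 558 events, power 0.750 (stated 0.93).
- 10 years: 1791 × 10 × 0.0519 = 930 events, power 0.925 (stated 0.98).
- 15 years: 1791 × 15 × 0.0519 = 1,394 events, power 0.986 (stated 0.99).

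Even on this ceiling, 948 events in 10,746 person-years would need a rate of 88.2 per 1000, not 51.9.

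**Step 2: the plan's own terms** (first events; 85% of those still event-free retained after year 6).
- 6 years: 1791 × (1 − e^(−0.3114)) = 479 events, power 0.685.
- 10 years: 479 + 0.85 × 1791 × e^(−0.3114) × (1 − e^(−0.2076)) = 479 + 209 = 688 events, power 0.833.
- 15 years: 479 + 0.85 × 1791 × e^(−0.3114) × (1 − e^(−0.4671)) = 479 + 416 = 895 events, power 0.916.

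Adding non-CV death as a competing event at 13.7 − 5.5 = 8.2 per 1000 person-years gives 0.675, 0.820 and 0.902. Reading 51.9 as the control-arm rate as well gives 0.64, 0.79 and 0.88.

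**Step 3: check of the method on the Update.** Use 1,791 to year 6, then the event-free share of 1,031 for nine more years: 479 + 1031 × e^(−0.3114) × (1 − e^(−0.4671)) = 479 + 282 = 761 events, power 0.868. With non-CV death it is 0.853 to 0.859, depending on whether the 1,031 are taken to be alive at year 6. The stated 86.3% reproduces to within about 1 point.

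**Step 4: the 0.00 cells.** Unconditional power of a two-sided 0.05 test cannot be below 0.05. First events over 6 years at the printed rates:
- CV mortality: 58 events, power 0.14.
- Microvascular: 308 events, power 0.50.
- Total mortality: 141 events, power 0.26.

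**Step 5: growth from year 10 to year 15 in the secondary rows.** Events implied by the printed powers:

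| Outcome | 10 years | 15 years | Ratio |
|---|---|---|---|
| CV mortality | 20.7 | 172 | 8.3 |
| Microvascular | 199 | 507 | 2.5 |
| Total mortality | 60.7 | 255 | 4.2 |

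Allowing for rounding of the printed powers, the ratios are still at least 7.0, 2.48 and 3.9. One constant rate gives at most 15/10 = 1.5-fold from randomization, or 9/4 = 2.25-fold if only post-trial years count. Post-trial counting comes near the 10-year cells (about 0.10, 0.31–0.34 and 0.17–0.18). It misses the 15-year cells (about 0.16, 0.56–0.64 and 0.32–0.33) and the primary row.

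**The case against.** **Another method may lie behind the primary row.** The plan describes its target as a 20% reduction in primary events. Taken as a comparison of two proportions with 85% of 1,791 (761 per arm) and 51.9 as the control rate, the 15-year figure is 0.989: control risk 1 − e^(−0.7785) = 0.541 against 0.433. With risk growing linearly, the 10-year figure is 0.983 (0.519 against 0.415). A reader might infer that 0.99 is unreachable under the 85% footnote; this shows that it is not. But no single form fits the row. The exponential form gives 0.908 at 10 years, and the linear form would print 1.00 at 15. With all 1,791 at 6 years they give 0.755 and 0.836. The linear form with a pooled rate gives 0.886, still short of 0.93. The table also says hazard ratio, and the endpoint is time to first event.

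**The 0.00 cells may be conditional power.** The reference list includes a paper on conditional power for deciding whether to extend a trial, and conditional power can be near zero. Nothing in the text ties it to Table 2, which is presented as expected power. It remains possible, and it would call for a label.

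**Hazards may rise as the cohort ages.** That could account for some of the growth in Step 5, but the table states one rate per outcome. For CV mortality the cells imply about 151 events in years 10 to 15, against 21 before.

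**The mortality sentence.** A reader might infer that better power, yet under 30%, contradicts the 15-year entries of 0.31 and 0.43. The documents do not establish this. The sentence names no horizon, cohort or rate, and rests on additional information that is not shown. At Table 2 rates, 1,031 subjects over 10 years give 0.13 and 0.25, above the printed 0.08 and 0.14 and below 0.30. With the Mortality Analysis Cohort of 1,639, total mortality at 10 years would be 0.37, so that reading does not carry over to it. This needs clarifying; it is not a shown error.

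**Consequence is small.** This stands. No test, alpha or sample size depends on these cells, the Update replaces the 15-year primary figure, and low mortality power is openly admitted.

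**Conclusion.** The point holds as a minor one. The primary cells at 6 and 10 years exceed what the stated rate and hazard ratio can give even at the ceiling (0.75 and 0.925, against 0.93 and 0.98). On the plan's first-event, log-rank terms the row is about 0.69, 0.83 and 0.92, or 0.675, 0.82 and 0.90 with non-CV death. The overstatement is about 24, 15 and 7 points without the mortality term. The 15-year cell is the weakest part: ignoring depletion and loss gives 0.986 and a two-proportion comparison gives 0.989, but neither matches the stated set-up. The 0.00 cells are wrong as unconditional power or lack a label, and the secondary rows do not follow from one constant rate.

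This rests on N = 1,791, 1:1 allocation and constant hazards. A reader might infer that the study is underpowered for its primary outcome. The documents do not support that: 86.3% reproduces, and recomputed power rises from about 0.69 at 6 years to about 0.87 for the achieved cohort. That rise agrees with the claims of improved power made elsewhere in the protocol.

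**What to change.** 1. Recompute Table 2 by one method and state it under the table: N, allocation, pooled or control-arm rate, retention, handling of competing death, first events only. By the method in Step 2, the primary row becomes about 0.69, 0.83 and 0.92 in place of 0.93, 0.98 and 0.99.
2. Give the three 0.00 cells their values or mark them *not applicable* with a reason. If they are conditional power, say so.
3. For the microvascular row, first replace the rate of 31.4. It belongs to the footnoted composite, which includes severe visual impairment and ischemic amputation. The Major secondary end-points section now lists end-stage renal disease or non-ischemic amputation, and the Updates under Missing Data analyse visual impairment separately. Values computed from 31.4, including the 0.50 above, should not be adopted.
4. As clarification only, have the mortality sentence name its cohort, horizon and updated rates, and the Table 2 entries it is compared with. Align the Study Significance statement about adequate power for mortality with the Update's admission that this power is poor, for example by describing the aim as estimating mortality effects with confidence intervals.

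The cost is text and one table; conduct and analysis do not change. The downside is that stated primary power becomes less favourable at all three horizons. At the printed rates, the 15-year CV mortality figure would also fall, from 0.31 to about 0.25.
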